6.9.1 Inclusion criteria

1. Patients must have a histologically confirmed diagnosis of NB with relapse in the CNS or LM.
2. Patients need to have progressed in CNS/LM through induction therapy or have relapsed in CNS/LM following induction. CNS/LM progression/ relapse is defined as LM disease or metastatic deposits in the CNS parenchyma, (excluding skull bone-based metastases).
3. Stable systemic disease not requiring chemo/ immunotherapy as judged by the investigator.
4. VP shunt (only shunts with programmable valves can be accepted) is allowed however should be closed (or adjusted to highest pressure setting) during IMP infusion. It is recommended that the VP shunt remains closed for approximately 5 hours after treatment and then readjusted. The shunt readjustment times are at the discretion of the treating physician. Closure of VP shunt is done at the discretion of the treating physician and the VP shunt should at any time based on patient safety evaluation be re-opened- at the assessment of the treating physician. Patients with ventriculo-atrial or ventriculo-pleural shunts are not eligible.
5. Patients must be between the ages of birth and 18 years at the time of screening.
6. Patients must have a life expectancy of at least 3 months as judged by the investigator.
7. Acceptable hematological status, defined as:
 - Hemoglobin ≥ 8 g/dL
 - WBC count $\geq 1000/\mu\text{L}$
 - Absolute neutrophil count $\geq 500/\mu\text{L}$
 - Platelet count $\geq 50,000/\mu\text{L}$
8. Acceptable liver function defined as:
 - ALT and/or AST ≤ 5 times UNL
 - Bilirubin $\leq 3 \times \text{UNL}$

In case either AST or ALT $\geq 3 \times \text{ULN}$, bilirubin must be $\leq 2 \text{ UNL}$
9. Acceptable kidney function defined as:
 - eGFR $>60 \text{ mL/min}/1.73 \text{ m}^2$ calculated by the 2009 revised Bedside Schwartz Equation (Appendix 3).

10. Written informed consent from legal guardian(s) and/or child must be obtained in accordance with local regulations. Pediatric patients must provide assent as required by local regulations.

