10.7 Expected side-effects related to ^{131}I -omburtamab and dexamethasone

^{131}I -omburtamab:

For detailed description, please refer to current IB.

The risks of ^{131}I -omburtamab include thyroid suppression, neutropenia and myelosuppression requiring red blood cell and/or platelet transfusions. Expected toxicities in the acute phase include the known risks associated with intraventricular infusions: headache, vomiting, and fever in the first few hours post-infusion.

Dexamethasone:

The expected toxicities of dexamethasone include lymphopenia, anemia and hyperglycemia.

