12.4 Safety Analysis

The safety analysis set will be used for all safety analyses. Adverse event data will be listed individually, and the incidence of adverse events will be summarized by system organ class (SOC) and preferred terms for each treatment group. AEs will be coded using the Medical Dictionary for Regulatory Activities (MedDRA) version 19.0 or later. AEs will be regarded as treatment-emergent adverse events (TEAEs) if they occur after first administration of ^{131}I -omburtamab. Related AEs are defined as adverse drug reactions (ADRs).

Listings will be made of all AEs, including non-TEAEs. All TEAEs, ADRs, SAEs and serious adverse reactions (SARs) will be summarized. The summaries will include number of events, number of patients, and percentage of patients reporting these events and will be tabulated by SOC and preferred term (PT). TEAEs will also be summarized by severity and by relationship to IMP. When calculating the incidence of adverse events, each adverse event will be counted only once for a given patient within a specified SOC, preferred term. If the same adverse event occurs on multiple occasions for a patient, the occurrence with the highest severity and relationship to IMP will be reported. Changes in vital signs, hematology, and clinical chemistry parameters from baseline to the end of the trial will be examined. Treatment-emergent changes from normal values to abnormal values in key laboratory parameters will be identified. Effects on cognitive functions will be assessed summarizing changes from baseline in performance testing results with descriptive statistics.

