Before signing the Informed Consent, the patient/parents must be given sufficient time to consider the possible participation. Further, each patient must be informed about their right to withdraw from the trial at any time. Parents and patients will also be informed that research participation is voluntary but if they withdraw from the trial, their data will still be used. When the informed consent form has been signed, the patient/parent(s) receives a copy of the signed form and the original is retained in the investigator site file. A second copy may be kept in the patient's medical notes. The informed consent forms must be signed and dated both by the signee and by the person providing the information to the patient/parents. It is recommended to notify the participant's family doctor of the participant's consent to participate in the trial.

13.4 Special considerations for patients having the Ommaya reservoir implanted at the referring hospital or locally but before entering the screening period.

The Ommaya reservoir is to be placed after the written informed consent has been obtained. In cases where placing of the Ommaya is considered in association with the surgical procedure that is recommended before enrollment in the trial, informed consent may be obtained up to three months before the start of the screening period. This is considered acceptable since placing of the Ommaya in association with the anesthesia induced for the surgical resection of the tumor will reduce the burden to the patient by avoiding an extra surgical procedure. Furthermore, the patient may receive high dose chemotherapy in the period leading up to the screening period which may be associated with myelosuppression and therefore rendering an invasive procedure like Ommaya placement not feasible.

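### The only categorical laboratory summary in section 12.4 counts changes from normal to abnormal, so a child who enters with a permitted abnormal value cannot be flagged for that parameter and no grade is shown

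*Combined protocol and SAP*

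**What the plan says.** Section 12.4 describes two analyses of laboratory data. The first is continuous in character: "Changes in vital signs, hematology, and clinical chemistry parameters from baseline to the end of the trial will be examined". The second is categorical: "Treatment-emergent changes from normal values to abnormal values in key laboratory parameters will be identified". No shift by CTCAE grade, worst post-dose grade or nadir is specified. Adverse events have their own severity table: "TEAEs will also be summarized by severity and by relationship to IMP".

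The entry criteria allow abnormal values. Inclusion item 7 in section 6.9.1, headed "Acceptable hematological status, defined as", sets floors of "Hemoglobin ≥ 8 g/dL", white cells 1000/µL, neutrophils 500/µL and platelets 50,000/µL. Item 8 accepts ALT or AST up to 5 times the upper normal limit and bilirubin up to 3 times.

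On treatment before entry, section 13.4 notes that "the patient may receive high dose chemotherapy in the period leading up to the screening period which may be associated with myelosuppression". Appendix 2 recommends, at the physician's discretion, craniospinal irradiation from week -10 and chemotherapy at week -5, with stem cell rescue if needed. Section 10.7 lists among the product's risks "neutropenia and myelosuppression requiring red blood cell and/or platelet transfusions".

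**The concern.** A normal-to-abnormal rule works when most patients start normal. Here the criteria and the recommended prior treatment make abnormal baselines foreseeable, and marrow suppression is both a consequence of that treatment and a named risk of the product. A child who enters with a low platelet count that then falls steeply is abnormal throughout and never meets the rule for platelets. The rule also treats a trivial departure from normal and a profound one alike.

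In a single-arm trial the shift within each patient, from baseline to worst value, is the natural way to separate an effect of the product from the residue of earlier therapy. The protocol itself thinks in grades: section 6.1.4 uses ongoing Grade 3 or 4 myelosuppression at week 4 as the ground for delaying cycle 2. No laboratory table described in section 12.4 would show those grades.

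**Working it through.** There is no stated figure to reproduce. The check sets the provisions side by side and adds one line of arithmetic.

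**1. Who can meet the flag.** For a given parameter, only children normal at baseline can. For liver tests, the text itself shows that abnormal entrants are allowed, because the limits are multiples of the upper normal limit. For blood counts, I assume that the item 7 floors lie below the laboratories' normal ranges, which the documents do not print. Exclusion item 8 in section 6.9.2 requires toxicity below Grade 3 only for non-hematologic organs, so it does not remove children with low counts.

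**2. What else would show the worsening.**

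| Provision | Includes children abnormal at baseline? | Shows grade or nadir? | Depends on judgement? |
|---|---|---|---|
| Normal-to-abnormal flag (12.4) | No, for that parameter | No | No |
| Change from baseline to end of trial (12.4) | Yes | Neither is named | No |
| Laboratory abnormality as an AE (10.1.1) | Yes | Grade | Yes: clinically significant and needing active management |
| Worsening of a pre-existing condition (10.6) | Yes | Grade | Yes: must be recognised and recorded |
| New AE at each change of grade (10.6.4) | Yes, once an AE is recorded | Grade | Yes, for the initial AE |

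A comparison of baseline with the end of the trial can miss a transient fall within a cycle. Blood products and growth factor, allowed in section 6.1.3, can blur it further. Section 11.1 requires Grade 4 laboratory values to be retested within 24 hours, which makes it more likely that they reach the AE record. No matching rule exists for Grade 3.

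**3. Size, for one parameter.** Let N be the number of children and q the share already abnormal at baseline for that parameter. The maximum number who can be flagged is N × (1 − q), rounded down. Section 6.8 gives N from 32 to 50. The documents give no q, so these values are assumptions.

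| q | N = 32 | N = 50 |
|---|---|---|
| 25% | 32 × 0.75 = 24 | 50 × 0.75 = 37.5, so 37 |
| 50% | 32 × 0.50 = 16 | 50 × 0.50 = 25 |
| 75% | 32 × 0.25 = 8 | 50 × 0.25 = 12.5, so 12 |

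These are ceilings on one flag for one parameter. They are not estimates of missed toxicity.

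**4. Whether the data exist.** Table 1 schedules hematology and clinical chemistry at screening and in each of weeks 1 to 8. A worst post-dose grade in each cycle can therefore be derived without further sampling.

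**The case against.** The strongest reply is that serious worsening is already captured. Section 10.1.1 defines active management broadly, to include further investigation and more frequent follow-up. A child whose platelets fell from 60,000 to 10,000/µL would very probably appear as an AE, be graded, and enter the severity table. Worsening of a pre-existing condition is reportable, and a change of grade opens a new AE. The change-from-baseline analysis has no restriction on the baseline value. All of this stands, and it limits the point to the laboratory summaries.

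A reader might infer that section 12.4 looks at laboratory toxicity through this flag alone, or that secondary endpoint 7 is biased downwards by a calculable fraction. The documents support neither. Endpoint 7 covers severe and serious AEs with clinically significant laboratory abnormalities, and so runs through AE reporting. The cycle 2 delay does not use the flag either. It would also be wrong to apply an assumed share of children with any abnormal count to a single parameter: a child with low hemoglobin and normal platelets can still be flagged for platelets.

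A reader might also take myelosuppression to be the main toxicity. Section 10.7 does not rank the risks, and section 10.4 does not list it among the AEs of special interest.

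Finally, section 12.1 leaves detail to the SAP, and no separate SAP text on laboratory data is supplied. Shift tables may therefore exist there. Even so, the rule in section 12.4 is stated, not merely left open, and as stated it is the wrong rule for this population.

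**Conclusion.** The point holds as a weakness in the laboratory summary. The one categorical rule leaves out, parameter by parameter, every child who starts abnormal, and it shows no severity for the rest. What is left uncovered is worsening from an abnormal baseline that the investigator does not judge clinically significant and in need of active management, or that is not visible in an ungraded change from baseline. Its size cannot be stated without a baseline distribution. The illustration of at most 24, 16 or 8 of 32 children flagged for a parameter rests wholly on the assumed shares of 25%, 50% and 75%. Section 13.4 and Appendix 2 make low counts at entry plausible, but neither describes counts at first dose. The primary endpoint is unaffected.

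**What to change.** Replace the normal-to-abnormal sentence in section 12.4 with a definition along these lines: a treatment-emergent laboratory abnormality is a worsening by at least one CTCAE grade from the last value before the first dose. Present it as shift tables of baseline grade against worst post-dose grade, by cycle, for hemoglobin, white cells, neutrophils, lymphocytes, platelets, ALT, AST, bilirubin and creatinine. Add, for each parameter, the number of children reaching Grade 3 or 4 whatever their baseline grade. If a separate SAP already specifies this, bring section 12.4 into line with it.

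The cost is a change of wording and a few more tables, with no new sampling, no burden on patients and no change to clinical management. The downside for the sponsor is that the cytopenia figures may look less favourable.

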12.5 Dosimetry Analysis

Spinal cord, brain and non-target ROI absorbed radiation doses will be estimated and CSF mean absorbed radiation doses will be calculated on the basis of nuclear imaging scans (whole-body planar gamma camera scans). Additionally, the mean absorbed radiation dose in CSF and blood will be calculated from CSF and blood radioactivity measured in CSF and blood samples taken at pre-defined timepoints (section 9.1.2.4) after the dosimetry and the treatment doses in cycle 1 from all patients enrolled before January 1st, 2019.

Individual and mean dosimetry data will be calculated per trial site and will be summarized with descriptive statistics.

12.6 Pharmacokinetic Analysis

The radioactivity measurements in CSF and blood that are used for calculation of the mean absorbed radiation dose after administration of the dosimetry and treatment doses are also used for pharmacokinetic analysis. C_{max} in blood is determined and the elimination half-life as well as the areas under the radioactivity vs. time curves are calculated.

Individual and mean pharmacokinetic parameter (if applicable) will be summarized with descriptive statistics for all patients and by trial site.

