	assessments, CSF analysis, and pre- and post ^{131}I -omburtamab performance testing. Performance testing will be performed at trial baseline, 3 months after the last ^{131}I -omburtamab infusion, and twice yearly thereafter at the discretion of the investigator.
IMP	Monoclonal antibody omburtamab is a murine immunoglobulin G1 (IgG1) antibody raised in BALB/c mice. Omburtamab recognizes tumor-associated antigen B7-H3. The purified antibody is stored in glass vials between -25 to -15°C. The patients will receive omburtamab antibody radiolabelled with radioactivity calibrated to 50 mCi per treatment cycle. There will be a treatment dose reduction for patients younger than 3 years of age.
Trial period and duration	Trial duration will be up to 3 years for each patient. Safety and efficacy assessments will be performed for 26 weeks after the first ^{131}I -omburtamab cycle, with long-term follow up for up to 3 years after start of treatment.
Statistical considerations	
An interim analysis to evaluate the dosimetry endpoint as well as available safety and efficacy data, will be performed on data from patients having received at least treatment cycle 1 (both dosimetry and treatment dose) prior to January 1st, 2020. Starting January 1st, 2020, no further patients will be administered dosimetry doses.
 
Final analysis will be performed when at least 32 treated patients have completed long-term follow-up (3 years or until death). OS rate at 3 years and its 95% confidence interval will be estimated using Kaplan-Meier methods. [REDACTED] PFS will also be analyzed using Kaplan-Meier methods. Dosimetry will be summarized with descriptive statistics (n, mean, median, standard deviation (SD), minimum, maximum).
 
Safety summaries will be provided for treatment exposure, patient disposition, adverse events, adverse events leading to discontinuation and serious adverse events, laboratory safety data (serum chemistry and hematology), vital signs, and physical examination. The incidence of adverse events will be tabulated and reviewed for potential significance and clinical importance.

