¹⁰ If CSF sample is positive for abnormal cells or outside reference ranges for any of the following: 1. total protein 2. glucose 3. cell count, it must be repeated within 4 weeks of the sample at screening. If abnormal CSF glucose (CTCAE \geq Grade 2) is obtained, a fasting serum glucose is to be obtained at next patient visit. At week 26, the CSF analysis should include cytology only.

¹¹ Treatment with potassium iodide and Cytomel should be initiated 1 week prior to each ¹³¹I- omburtamab infusion in a cycle and continue until 2 weeks after ¹³¹I- omburtamab infusion in the same cycle..

¹² Thyroid protection should be initiated 1 week prior to IMP administration. See section 7.2.5 for further details.

¹³ Thyroid protection should be initiated 1 week prior to next IMP administration – this is only applicable for week 4 and not week 8. See section 7.2.5 for further details.

¹⁴ Beginning 24 hours before ¹³¹I-omburtamab administration please see section 6.1.2.

¹⁵ Given 1-2 hours prior to ¹³¹I-omburtamab administration, including oral acetaminophen/paracetamol and antihistamine (e.g., diphenhydramine), please see section 6.1.2¹⁶
Drawn and held for culture if elevated body temperature after dosing suggests infection rather than expected response to intracerebroventricular dosing.

¹⁷ Dose reduction: 50% (25 mCi) for patients < 1 of age and 33% (33.5 mCi) for patients age 1 year to < 3 years of age, respectively.

¹⁸ Non-SAE's captured from signing the informed consent form (ICF) to dosing should be recorded as medical history. AEs should be reported until 3 weeks after the last IMP administration. SAE's should be captured from signing the ICF. Starting at week 4 (for patients receiving only one cycle) and starting at week 8 (for patients receiving both cycles) only SAEs considered related to ¹³¹I-omburtamab or new onset of cancers regardless of causality should be reported.

¹⁹ Limit to therapy related to cancer.

²⁰ In case fertile women (experienced menarche prior to screening or during treatment, until week 8) are enrolled; pregnancy testing should take place at screening, at week 4 and week 8, and at follow-up at week 26.

²¹ Follow-up at week 26 (24-29 weeks after first treatment) and Long-term follow-up visits at Weeks 52, 78, 104, 130 & 156 (\pm 4 weeks) can be done at referral site.

²² If done at referral site imaging parameters as required in the Imaging Manual should be followed to the extent possible.

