7 TREATMENTS

7.1 Investigational Medicinal Product

Screening assessments will be evaluated before any patient receives IMP. The patient and/or legal guardian must have received patient information and signed the ICF. Eligible patients must meet all inclusion criteria and must not violate any of the exclusion criteria (please see sections 6.9.1 and 6.9.2).

Monoclonal antibody omburtamab is a murine IgG1 antibody that is raised in BALB/c mice and recognizes tumor associated antigen B7-H3. Omburtamab will be radiolabeled with iodine-131 at a radiopharmacy connected to the treating institution or at a designated central radiopharmacy. At each clinical site, the ^{131}I -omburtamab dose should be assayed immediately prior to administration to verify that the prescribed activity and the activity actually administered agree within 10%. The residual activity in the dose syringe should then be assayed following administration to determine the net activity administered (= pre-administration activity – post-administration residual activity). The amount of radioactivity infused in patients should be assessed by measuring radioactivity of the infusion syringe before and after ^{131}I -omburtamab infusion into the indwelling intraventricular access device (e.g. Ommaya) and subtracting before and after counts. The radiolabeled ^{131}I -omburtamab is sterile filtered before administration. Patients will receive up to two cycles of ^{131}I -omburtamab.

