8.1.2 Secondary endpoints

1. CNS/LM PFS at 6 and 12 months will be estimated based on the time from first treatment dose to CNS/LM progression or death from any cause. Patients alive without CNS/LM progression at time of analysis, will be censored at last date of disease evaluation without evidence of progression.
2. OS at 12 months will be estimated based on the time from first treatment dose to death by any cause. Patients alive at time of analysis, will be censored at last date known to be alive.
3. ORR assessed as a combination of partial response and complete response as defined by the Response assessment in Neuro-Oncology (RANO) group criteria for brain metastasis (Lin et al, 2015) or leptomeningeal metastases as defined by EANO-ESMO criteria (Le Rhun et al, 2017). ORR will be assessed at 6 months after the first treatment dose of ^{131}I -omburtamab
4. ORR according to CSF cytology. Response is defined as a complete response when CSF converts from positive at baseline to negative after treatment with ^{131}I -omburtamab
5. Whole-body, organ, blood, and CSF radiation dosimetry.
6. Pharmacokinetic analysis of activity in blood and CSF including derivation of best-fit uptake and/or clearance parameters (half-times, maximum value) of time-activity concentration curves and of I-131 residence times (i.e., cumulated activity) concentrations (in $\mu\text{Ci}\cdot\text{h/g}$).
7. The frequency, type, and duration of treatment-emergent severe adverse events and serious adverse events, including clinically significant laboratory abnormalities. All adverse events will be graded according to Common Terminology Criteria for Adverse Events (CTCAE), version 4.0.
8. Performance assessment to monitor gross changes in neurological function is performed at week 26 and subsequently every 6 months during trial period.
9. The rate of ADA occurrence assessed three weeks after the first and second treatment dose of ^{131}I -omburtamab

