9.1.2.7 ***Anti-Drug-Antibody effects on PK and Safety.***

The ADA characterization will deliver occurrence rate of neutralizing antibodies in blood and cerebrospinal fluid (CSF) of exposed patients. Potential associated effects of any neutralizing ADA's on ^{131}I -omburtamab pharmacokinetics (PK) in blood and CSF and safety will be investigated.

9.1.2.7.1 *ADA effects on PK*

Radioactivity counts in blood and CSF will be measured at the following time points after treatment with ^{131}I -omburtamab:

- 1h after treatment
- 6h after treatment
- 24 after treatment
- 7 days after treatment.

The analysis will comprise an intra-patient comparison of PK parameters from the two dose administrations in patients with and without presence of neutralizing ADAs in blood or CSF.

9.1.2.7.2 *ADA effects on Safety*

The analysis will comprise a comparison of reported safety events after the second dose administration in patients with and without presence of neutralizing ADAs in blood or CSF.

9.2 **Other assessments**

9.2.1 **Hematology and clinical chemistry**

Hematology and clinical chemistry will be measured by a local laboratory during screening and in all following treatment cycles and will assess liver and kidney function (ALT, AST, alkaline phosphatase, albumin, bilirubin, BUN, glucose and creatinine), total protein and serum electrolytes (sodium, potassium, chloride and bicarbonate). Complete differential blood count, including eosinophils and platelets, will be performed during screening and in the cycles up to the follow-up at week 26. Thyroid stimulating hormone (TSH)/ free and total T4 to be assessed at screening, pre-dose week 1 and 4, pre-dose week 5 and 8, week 26 if applicable and weeks 52, 78, 104 130 and 156..

If abnormal serum glucose (CTCAE \geq Grade 2) is obtained, a fasting serum glucose is to be obtained at next patient visit. AE reporting of hyperglycemia will require fasting values to assess CTCAE grading.

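### Pooled and by-site means of Cmax, AUC and cumulated activity mix administered activity with kinetics; values per unit of net administered activity should be added and the residence-time term corrected

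*Combined protocol and SAP*

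**What the plan says.** Section 12.6 derives Cmax in blood, elimination half-life and areas under radioactivity-time curves from samples taken after both dosimetry and treatment doses. On reporting it says: "Individual and mean pharmacokinetic parameter (if applicable) will be summarized with descriptive statistics for all patients and by trial site".

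Secondary endpoint 6 (synopsis and 8.1.2) covers half-times, maximum values and "I-131 residence times (i.e., cumulated activity) concentrations", in µCi·h/g.

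The synopsis sets "radioactivity calibrated to 50 mCi per treatment cycle". Table 1, footnote 17, gives the reductions: "Dose reduction: 50% (25 mCi) for patients < 1 of age and 33% (33.5 mCi) for patients age 1 year to < 3 years". Eligibility runs from birth to 18 years (6.9.1), so all three levels can occur.

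For anti-drug antibodies (ADA), section 9.1.2.7.1 says: "The analysis will comprise an intra-patient comparison of PK parameters from the two dose administrations", in children with and without neutralizing ADA. Its data are radioactivity counts in blood and CSF at 1 h, 6 h, 24 h and 7 days. It does not say whether the comparison is a ratio or a difference.

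Section 7.2.3 allows each unit dose to lie within ±10% of the intended activity. Section 7.1 has the syringe assayed before and after infusion "to determine the net activity administered". No pharmacokinetic section uses that number.

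**The concern.** Cmax, AUC and cumulated activity concentration all scale with the activity given. When children receive different activities, an average of these quantities reflects who was enrolled as well as how the antibody is distributed and cleared. Two sites with identical kinetics will show different means if their age mix differs, and a reader could take that for a site or handling effect.

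The endpoint wording adds an ambiguity. Residence time is cumulated activity divided by administered activity, so it is a time. A value in µCi·h/g is time-integrated activity per gram and has not been divided by dose. The text names one quantity and gives the unit of the other.

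The comparison of the first and second dose is where the plan looks for an effect of neutralizing ADA on exposure. Variation in syringe activity enters Cmax and AUC there although it has already been measured and could be removed.

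**Working it through.** **Inputs.** Full activity 50 mCi (synopsis); reductions of 50% and 33% (Table 1, footnote 17); tolerance ±10% (7.2.3); physical half-life of iodine-131 8 days (4.2.1). The share of children at each level is not given, so it is an assumption shown over a range. The dosimetry-dose activity is not in the available text and is left out of the figures.

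**1. The plan's own figures.** 50 × (1 − 0.50) = 25.0 mCi and 50 × (1 − 0.33) = 33.5 mCi. Both reproduce.

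**2. Spread of planned activity.** 50/25 = 2.0; 50/33.5 = 1.49; 33.5/25 = 1.34. At the tolerance limits, 55/22.5 = 2.44.

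**3. Effect on a pooled mean.** Assume identical kinetics and equal distribution volume at all ages, so that exposure is proportional to activity. With shares p at activities d, the mean is m = Σp·d and CV = √(Σp(d − m)²)/m. For shares of 10/30/60% at 25/33.5/50 mCi:

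- m = 2.5 + 10.05 + 30 = 42.55, which is 0.85 of the 50 mCi value.
- Variance = 0.1 × 17.55² + 0.3 × 9.05² + 0.6 × 7.45² = 30.8 + 24.6 + 33.3 = 88.7; SD = 9.42; CV = 22%.

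| Assumed shares 25/33.5/50 mCi | Mean relative to 50 mCi | CV from activity alone |
|---|---|---|
| 0/10/90% | 0.97 | 10% |
| 5/20/75% | 0.91 | 18% |
| 10/30/60% | 0.85 | 22% |
| 20/40/40% | 0.77 | 26% |

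A site with only children aged 3 or over has relative mean 1.00. A site with the 10/30/60% mix has 0.85 from the same kinetics.

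**4. Distribution volume.** Concentration is proportional to activity divided by volume. At 25 versus 50 mCi the ratio is 0.5 if volumes are equal. If the younger child's volume were half as large (an assumption), it would be 0.5/0.5 = 1.0.

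**5. Dose 2 against dose 1 within a child.** With the same intended activity at both doses, the level cancels in a ratio. The tolerance leaves 0.9/1.1 = 0.82 to 1.1/0.9 = 1.22. If activity is uniform within tolerance (an assumption), the simulated 95% range is 0.86 to 1.17. Dividing each value by its own net activity brings this part to 1.00. If absolute differences are used instead, a true 20% fall is 5, 6.7 or 10 units at the three levels, and the level mix returns.

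**6. Why decay correction should be stated.** Effective half-life = 1/(1/Tb + 1/8), with Tb the biological half-life in days. For an assumed fall in Tb from 8 to 4 days, the effective half-life goes from 4.0 to 2.67, a ratio of 1.5 rather than 2. For a fall from 1 to 0.5 day it goes from 0.889 to 0.471, a ratio of 1.89. The blunting depends on Tb, which the documents do not give.

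**The case against.** The strongest reply is that absolute exposure is what matters for a radiotherapeutic, and that the age reductions may be there to offset smaller volumes. Section 5.2.1 calls the adjustment usual for this route, and the reference list includes an intrathecal methotrexate regimen based on age-related pharmacokinetics. Absolute concentrations might then be similar across levels, and per-mCi values would differ. This stands against reading the 2.0-fold spread in activity as an established 2.0-fold difference in exposure, and against pooling only normalised values. It does not defend a single pooled mean, because only both scales together, split by level, would show whether such an offset exists.

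Four other inferences are tempting but not supported:

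- **The activity mix distorts the ADA comparison.** It is within-patient, so the mix cancels in a ratio. Nothing links syringe variation to ADA status, so the tolerance adds noise, not bias between ADA groups.
- **Children change activity level between doses.** No section says the level is re-set for cycle 2, and a first or third birthday would have to fall in the interval.
- **Counts are not decay-corrected.** The documents are silent. Section 11 refers measurement to manuals and has the parameters calculated centrally.
- **All parameters are affected.** Half-life does not depend on administered activity.

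It is also fair that section 12.1 leaves detail to the SAP, that individual values are reported as well, that means are given only if applicable, and that the stated unit already shows which quantity endpoint 6 reports. However, the combined document contains no further pharmacokinetic analysis text, and the endpoint wording is the protocol's own.

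**Conclusion.** The point holds for pooled and by-site means of Cmax, AUC and cumulated activity concentration. The 2.0-fold spread in planned activity follows directly from the documents. The 10% to 26% CV rests on assumed age shares, identical kinetics and equal distribution volume; it would be smaller if volume falls with age in step with activity. Dosimetry-dose samples may add a further level of unknown size.

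For the ADA comparison the conclusion is narrower: a removable source of noise in Cmax and AUC, provided a ratio is used. On decay, the plan should state its choice; the text does not show that the choice is wrong.

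These are descriptive secondary summaries. The primary endpoint is untouched. The case for change is that the better analysis uses data already collected.

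**What to change.** - **8.1.2 item 6 (and the synopsis) and 12.6:** keep the absolute values. Add Cmax, AUC and cumulated activity concentration divided by the net administered activity of that dose, for example µCi·h/g per mCi.
- **12.6:** present absolute values by activity level, with dosimetry-dose and treatment-dose values separate. Use the normalised values where patients or sites are pooled for comparison.
- **9.1.2.7.1:** define the comparison as a within-patient dose-2/dose-1 ratio of activity-normalised parameters. State that it uses decay-corrected counts, with uncorrected values kept for dosimetry.
- **8.1.2 item 6 (and the synopsis):** replace the residence-time phrase with cumulated activity concentration, which matches the stated unit.

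The cost is a wording change, a few derived variables and some extra table rows. No new sample or visit is needed, treatment is unaffected, and no absolute exposure information is lost.
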